If **CHALO! 2.0** is even modestly effective, it could have a large population level impact given its rapidly scalable design. **CHALO! 2.0** is designed to address the limitations presented by previous SMT-based interventions, by using a widely adopted existing technology medium (WhatsApp) that is already integrated into individuals' daily routines, delivering contents that are incorporated into typical use patterns and pushed to users, using diverse digital media (brief video clips, pictures, infographics, text messages, website links) to facilitate behavior change and allow heterogeneity in learning, allowing participants to message peer-counselors 'just-in-time' to obtain information or support as desired, and drawing on evidence from social media marketing to develop contents specific to how individuals process SMT information to maximize behavior change.⁵⁰⁻⁵³ Finally, **CHALO! 2.0**'s design features protect against shifting use of online technology, making findings from this study applicable for the future. For example, **CHALO! 2.0** will use a generalizable communication system (WhatsApp) with core contents and design features that are easily scalable to other messaging platforms (e.g., Viber, Facebook Messenger, multimedia SMS, Apple watch). This will help ensure relevancy, acceptability, and feasibility for future scale-up, increasing likelihood of impact.^{36,37,54-56}

Aims:

1. To determine whether CHALO! 2.0 increases HIV testing compared to control conditions, and to identify factors associated with HIV testing.
2. To determine whether CHALO! 2.0 increases linkage-to-care (both HIV prevention through counseling

and use of PrEP, and HIV treatment with antiretrovirals), and to identify factors associated with linkage to care.

Methods

Research Sites:

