- Secondary outcomes: HIV treatment linkage (yes/no) and ART initiation (yes/no) for those testing HIV positive, each variable individually in the primary composite outcome (i.e. counseling, PrEP), sexual behavior (consistent condom use, number of partners).
- Exploratory Outcomes: include alcohol/substance use, PEP use, STI testing/treatment, and type of prevention or treatment care site accessed (i.e. HST vs. other).

Finally, the following outcomes will be reported by study arm: HIV knowledge, HIV- and MSM-stigma, risk-perception, self-efficacy, social support, intention to obtain HIV test in next one month, and SMT engagement by arm (proportion of all messages viewed, website visit, and any communication with online-peer counselors).

11. Plans to identify contamination across study arms. Contamination will be assessed by using a content recall questionnaire^{86,87} to measure any diffusion and sharing of **CHALO! 2.0** and attention matched control contents, determining whether participants report sharing messages or website links. Participants will also be asked if they knew anyone participating in the study and if they received any contents from them.⁹⁵ Members from the HST and Einstein research teams will assist in building research instruments.

12. Randomization checks and missing data. A member from either the Einstein or HST team will first review and summarize data using descriptive summaries and graphical analyses to ensure that reported values are within appropriate ranges, check for outliers and abnormal values, and verify that distributions of measures meet

assumptions of planned statistical tests. The Einstein and HST research teams will also explore whether **CHALO! 2.0** and the 2 control groups are equivalent on potential confounders (e.g., sexual identity, income, age, education, intention to test, and sexual behaviors. If these variables differ between groups, we will include them as covariates in multivariable analyses (see Section C.7.4). For missing categorical data, we will use multivariate multiple imputation using the fully conditional specification method.⁹⁶ We will repeat imputations 5 times, and then compare statistical results using datasets that include imputed values and the dataset that drops missing values. This will guide interpretation of our assessment of the impact of missing data on our study findings, as well as our interpretation of overall results.

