>99%	0.15-0.4	0.05-0.1	0.03-0.01
>98%	0.3-0.4	0.1-0.2	0.03-0.01
>90%	0.3	0.15	0.1-0.15
>70%	0.2	0.1	0.08
>49%	0.3	0.2	0.2
>21%	0.15	0.1	0.1

*power is for CHALO! compared to each control separately

months, explore

whether participant factors and testing strategy predict HIV prevention (counseling or PrEP use) and treatment (ART initiation). For secondary and exploratory outcomes (defined in C7.1), we will repeat analyses as above, using ANOVA for or chi-square tests as appropriate.

13.4 Aim 2 sample size considerations: We anticipate that there will be no higher than 7% prevalence of undiagnosed HIV. Combined with expected HIV testing rates by 12 months of at least 75%, 45%, and 35% in the three arms, we anticipate the available sample size of HIV-uninfected participants for Aim 2 to be **CHALO! 2.0** ($n_1=247$), attention-matched control ($n_2=139$), and digital coupon ($n_2=108$). Based on HST's current linkage-to-care rates for HIV- negative individuals (30%),⁹⁰ we expect the rate of linkage-to-prevention care at 12 months to be 30% for **CHALO!** vs. 15% for attention-matched control vs. 5% for digital coupon only. The study's 2 main effects (**CHALO!** vs. Attention-matched control and **CHALO! 2.0** vs. digital coupon only) have >90% and >99% power, respectively (Table 4). We also provide power estimates for smaller effect sizes. The power was calculated using PASS software V15.0., with a two-tailed alpha of .025, resulting in a family-wise error rate of at most 0.05 for the primary outcome in the Aim 2. Due to an expected overall small number of individuals testing HIV- positive, we will not have power to detect potential differences between arms.

PROTECTION OF HUMAN SUBJECTS

A. RISKS TO HUMAN SUBJECTS

A1. HUMAN SUBJECTS INVOLVEMENT, CHARACTERISTICS, AND DESIGN.

A1a. Proposed human subject involvement. The protocol will include a 3-arm parallel, single blind, pragmatic randomized control trial of an online HIV digital messaging intervention (CHALO! 2.0) compared to an Attention-Matched Control, or a Digital Coupon only. Through online surveys, HIV testing utilization and results, and clinic visit data tracked by HST healthcare workers during the 12-week intervention period, and during the 15 months of follow-up, we will evaluate the outcomes for CHALO! 2.0.

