A1b. Subject population characteristics. The 1000 MSM in the proposed trial will be composed of a diverse sample of individuals unaware of their current HIV status (e.g. never tested or tested >6 months ago and have been sexually active with men) recruited via MSM specific dating apps (Blued, Grindr), and via the most used general social media sites (Instagram) in an urban area with high rates of HIV (Mumbai, India). Currently, HIV rates for online-person recruited MSM in Mumbai are estimated at 5-7%, based on our recent studies (the only

such data available). All participants are expected to identify as Asian Indian and male.

A1c. Description and justification of sampling plan, recruitment and retention strategies and eligibility criteria.
Recruitment will be passive via online advertisement displayed to individuals on MSM dating apps (Grindr and Blued, and will include others if we find a new app emerging in popularity) or by targeted advertisements on Instagram to men who have LGBTQ/gay interests or keywords associated with their profiles. Due to technological advancements, the ads will be geographically limited to those potential participants accessing these sites from Mumbai or those who have indicated a Mumbai address on their social media profile. All advertisements will contain links directing potential participants contain links directing potential participants to a webpage with further information about the study and an eligibility screener. Eligible participants will be directly linked to an informed consent page (including an audio-video version of the informed consent),⁶³ and non-eligible participants will be directed to an exit page thanking them for their interest. Eligible participants who agree to participate after reading the informed consent will be directed to a baseline survey. All potential participants will provide a phone number associated with their WhatsApp account and an email address, and reply to a confirmation code (sent immediately to confirm the individual is real and not a bot or a computer program). Phone numbers will be checked against HST's registry by research staff to ensure participants aren't already receiving services through HST. Eligible participants will receive their incentive and be considered fully enrolled within 48 business hours.

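### Treatment linkage and ART initiation are compared between arms only among men who test positive, so the comparison omits any effect of CHALO! 2.0 that acts through testing

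*Combined protocol and SAP*

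**What the plan says.** The Aims section puts HIV treatment inside the Aim 2 question: linkage to care covers prevention through counselling "and use of PrEP, and HIV treatment with antiretrovirals), and to identify factors associated with linkage to care".

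Section 10 lists the treatment outcomes among the Aim 2 secondary outcomes: "HIV treatment linkage (yes/no) and ART initiation (yes/no) for those testing HIV positive". A man who does not test has no value for either.

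Section 13.3 gives their analysis: "For secondary and exploratory outcomes (defined in C7.1), we will repeat analyses as above". The analyses above are chi-square comparisons of study arms and logistic regression with arm as the main predictor.

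Section 13.4 supplies the inputs that show how large the restriction is: "We anticipate that there will be no higher than 7% prevalence of undiagnosed HIV", and "expected HIV testing rates by 12 months of at least 75%, 45%, and 35% in the three arms". It also concedes that few men will test positive and that arm differences among them cannot be detected.

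Two other statements bear on the point. Section 13 promises intention-to-treat analysis, but for primary analyses only. Section 13.3 also plans a whole-cohort exploration of ART initiation, but the predictors named are participant factors and testing strategy; study arm is not among them.

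**The concern.** The denominator is fixed after randomisation by a variable that the intervention is designed to change. Testing within 6 months is the Aim 1 primary outcome, and the plan expects testing by 12 months to differ by 30 and 40 percentage points between CHALO! 2.0 and the two controls. An infected man who never tests is not on treatment, yet he is left out and not counted as untreated, and this happens more often in the control arms.

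Two things follow. First, the main route by which CHALO! 2.0 could bring men to treatment (more infected men found) cancels from the comparison. Second, the groups compared are no longer randomised groups: men who test positive under CHALO! 2.0 may differ from those who test positive under a control condition.

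At stake is the treatment half of Aim 2. A trial that brought clearly more men to treatment could report no difference on the only treatment outcomes it defines.

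**Working it through.** **Inputs**

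- Randomised: 1,000 (Participants), about 333 per arm assuming equal allocation.
- Undiagnosed HIV: at most 7% (section 13.4); 5-7% in online-recruited men (section A1b). I use 5% and 7%.
- Tested by 12 months: at least 75% (CHALO! 2.0), 45% (attention-matched) and 35% (coupon only) (section 13.4). These are lower bounds, used here as point values.
- Linkage among men testing positive, L: not given in the documents, so an assumption, varied from 50% to 100%.
- Infected men are assumed to test at the same rate as others in their arm.

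**The plan's own figures from these inputs**

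The plan gives no expected count for treatment. It does use the same testing rates and prevalence for its HIV-uninfected sample of 247, 139 and 108:

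- Attention-matched: 333 × 0.45 × 0.93 = 139.4. Reproduces.
- Coupon only: 333 × 0.35 × 0.93 = 108.4. Reproduces.
- CHALO! 2.0: 333 × 0.75 × 0.93 = 232.3, not 247. The stated figure matches 266 × 0.93 = 247.4, that is, 12-month retention with no testing factor. This is a separate discrepancy and is not used below.

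**Men who can be scored**

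Scorable = 333 × prevalence × testing rate.

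| Prevalence | Infected per arm | CHALO! 2.0 | Attention-matched | Coupon only |
|---|---|---|---|---|
| 5% | 16.7 | 12.5 | 7.5 | 5.8 |
| 7% | 23.3 | 17.5 | 10.5 | 8.2 |

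At either prevalence, 25%, 55% and 65% of infected men have no value.

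**Equal linkage among diagnosed men**

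With the same L in every arm, the planned contrast is L − L = 0. Men linked per arm are 333 × prevalence × testing rate × L, so the ratios do not depend on L or prevalence:

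- vs attention-matched: 0.75 / 0.45 = 1.67
- vs coupon only: 0.75 / 0.35 = 2.14

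Example at 7% and L = 70%: the planned contrast is 70% vs 70% vs 70%, while 12.2, 7.3 and 5.7 men are linked.

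**When the direction would reverse**

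The conditional proportion favours control when L(CHALO!) < L(control). CHALO! 2.0 still has more men linked when 0.75 × L(CHALO!) exceeds the control testing rate × L(control). Both hold when L(CHALO!) / L(control) lies

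- between 0.45 / 0.75 = 0.60 and 1 (attention-matched)
- between 0.35 / 0.75 = 0.47 and 1 (coupon only)

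Example at 7%, with L = 70% under CHALO! 2.0 and 80% under control: the planned contrast is 10 points against CHALO! 2.0, while 12.2 men are linked against 8.4 (attention-matched) or 6.5 (coupon only).

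**Power with all randomised men as denominator**

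Two proportions, 333 per arm, two-sided alpha 0.025, each proportion = prevalence × testing rate × L, same L in each arm. The section 13.4 alpha is stated for the Aim 2 primary outcome and is borrowed here.

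| Prevalence, L | Linked, % of randomised | Power vs attention-matched | Power vs coupon only |
|---|---|---|---|
| 5%, 50% | 1.88 / 1.13 / 0.87 | 7% | 13% |
| 7%, 70% | 3.67 / 2.21 / 1.71 | 13% | 25% |
| 7%, 100% | 5.25 / 3.15 / 2.45 | 19% | 36% |

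These are normal approximations. Summing exact binomial probabilities for the pooled z test moves them by about a point, so the range is about 7-19% and 12-37%.

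**The case against.** **No conclusion turns on it.** The outcomes are secondary, section 13.4 already concedes lack of power, and the repaired comparison is also underpowered. This stands as a limit on importance. It does not answer the point: the concession is about precision, whereas here the quantity estimated is not the one Aim 2 asks about, and more participants would not change that.

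**Linkage among the diagnosed is a recognised measure.** The Background cites 90-90-90, whose second step is linkage among those aware of their status, and the testing step is compared under Aim 1. If numerators and denominators are printed, a reader can see the extra men treated. This is fair, and is why the conditional figure should be kept. It remains a cascade description and not a randomised comparison of treatment uptake.

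**A whole-cohort ART analysis is planned.** It is, so the variable is evidently meant to exist for everyone. Arm is not named as a predictor, so it does not fill the gap.

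**Small expected counts.** A reader might add that chi-square tests are invalid with so few men. The plan largely meets this: section 13.3 says "we will repeat analyses as above, using ANOVA for or chi-square tests as appropriate", and section 12 commits to checking test assumptions.

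**Reversal.** A reader might infer that the planned comparison will show harm because prompted testers link less readily than self-motivated ones. The documents give no linkage rates for HIV-positive men and nothing to suggest such a difference. All arms have the same coupon, peer counsellors and linkage protocols, and the community health worker is blinded to arm. Reversal is possible, not shown to be likely.

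**Counting everyone else as no has its own risk.** Men lost to follow-up, or treated outside the community partner's network, may be wrongly scored. Section 8.3 warns that some will not share outside-care information, and section 12 plans imputation for missing categorical data. This stands, and the fix must deal with it.

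**Conclusion.** The concern holds as a fault in what is estimated. Section 10 restricts the treatment outcomes to a post-randomisation group whose size the intervention is expected to change, section 13.3 compares arms within that group, and no comparison of treatment by arm among all randomised men is described.

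Its size rests on the plan's testing rates: with any common linkage rate, a true ratio of 1.67 or 2.14 in men linked appears as no difference. That result needs equal linkage among diagnosed men and testing by infected men at the arm's overall rate; it does not depend on the prevalence or on the linkage rate itself. The counts (about 12-17, 7-10 and 6-8 scorable men) do depend on prevalence, for which 7% is the plan's upper bound.

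The stronger reading, that the analysis will reverse the effect, is not supported: it needs lower linkage among CHALO! 2.0 positives, within the ratios shown, or chance with so few men. The Aim 1 primary outcome and the Aim 2 prevention outcome are not touched by this point. The change is worth making for a valid target and direction; it will not give adequate power.

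**What to change.** - In section 10, define HIV treatment linkage and ART initiation by 12 and by 18 months for all randomised participants: yes = documented linkage or documented ART start; no for men never tested.
- State that men lost to follow-up with no record count as no in the main version. Add one sensitivity analysis under the section 12 imputation and one that adds self-reported outside care.
- In section 13.3, report for each comparison the number per arm, the risk difference and an exact 95% CI.
- Keep the proportion among men testing positive, with numerators and denominators, as a descriptive step of the care cascade without a between-arm test.

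**Cost.** SAP wording, one table and two sensitivity analyses. No new data: linkage and ART status already come from the community partner's information system, the healthcare worker log and the surveys. The percentages will be small (about 1-5% of those randomised in the scenarios above), and the comparison stays underpowered, which the report should say. Never-testers' HIV status need not be known, because randomisation balances prevalence between arms in expectation. One risk remains: if treatment is recorded more completely for men who test through the trial's own sites, the all-randomised contrast could also be biased, which the self-report sensitivity analysis is there to probe.

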Power	CHALO! 2.0 ($n_1=300$)	attention-matched control ($n_2=300$)	Digital coupon only ($n_2=300$)
>99%	0.5-0.75	0.2-0.5	0.15-0.45
>93%	0.5-0.6	0.35-0.45	0.35-0.45
>59%	0.5-0.6	0.4-0.5	0.4
>15%	0.5	0.45	0.45

*power is for CHALO! compared to each control separately

report HIV- testing, or condition,

13.2 Aim 1 sample size considerations: With a total of 1,000 participants, we expect at least 900 participants at 6 months, and 800 participants at 12 months. This will provide a total of 300 participants per arm at 6 months, and 266 participants per arm at 12 months. Based on findings from online intervention studies of HIV testing showing 1.7-2.2 increases in odds of testing in intervention vs. control conditions (across low and high income countries and heterogeneous online interventions),⁹⁷⁻¹⁰⁰ we estimate the proportion HIV testing at 6 months to be 70% for **CHALO! 2.0** ($n_1=300$) vs. 35% for attention-matched control ($n_2=300$) and 30% for digital coupon only ($n_2=300$). With the expected sample, the study's 2 main effects (**CHALO! 2.0** vs. attention-matched control and **CHALO! 2.0** vs. digital coupon only) have >99% power (Table 3). We also provide power estimates based on a wider range of parameters in Table 3, showing that we have sufficient power to detect between-group differences in the primary outcome with smaller effect sizes. Power was calculated using PASS software V15.0, with all analyses conducted with a two-tailed alpha of .025, resulting in a family-wise error rate of at most 0.05 for the primary outcome.

13.3 Aim 2 analyses: To test the hypothesis that **CHALO! 2.0** participants will be more likely to be linked to care (vs. controls), we will compare rates of linkage-to-prevention (i.e. counseling, PrEP-initiation) at 12 months among HIV-uninfected participants between study arms. As for Aim 1, we will perform 2-sample comparisons of proportions using chi-square tests, and will also perform logistic regression with linkage-to-prevention by 12 months as the outcome and study arm as the primary predictor, adjusting for covariates in Table 2 as required. We will repeat these analyses with linkage-to-care outcomes at 18 months, and with the outcome of self-reported linkage-to-prevention by 18 months. Additionally, using the entire study cohort, we will

Table 4. Proportion linked to HIV prevention by 12 months

Power	CHALO! 2.0 ($n_1=247$)	attention-matched control ($n_2=139$)	digital coupon only ($n_2=108$)
>99%	0.15-0.4	0.05-0.1	0.03-0.01
>98%	0.3-0.4	0.1-0.2	0.03-0.01
>90%	0.3	0.15	0.1-0.15
>70%	0.2	0.1	0.08
>49%	0.3	0.2	0.2
>21%	0.15	0.1	0.1

*power is for CHALO! compared to each control separately

months, explore

whether participant factors and testing strategy predict HIV prevention (counseling or PrEP use) and treatment (ART initiation). For secondary and exploratory outcomes (defined in C7.1), we will repeat analyses as above, using ANOVA for or chi-square tests as appropriate.

13.4 Aim 2 sample size considerations: We anticipate that there will be no higher than 7% prevalence of undiagnosed HIV. Combined with expected HIV testing rates by 12 months of at least 75%, 45%, and 35% in the three arms, we anticipate the available sample size of HIV-uninfected participants for Aim 2 to be **CHALO! 2.0** ($n_1=247$), attention-matched control ($n_2=139$), and digital coupon ($n_2=108$). Based on HST's current linkage-to-care rates for HIV- negative individuals (30%),⁹⁰ we expect the rate of linkage-to-prevention care at 12 months to be 30% for **CHALO!** vs. 15% for attention-matched control vs. 5% for digital coupon only. The study's 2 main effects (**CHALO!** vs. Attention-matched control and **CHALO! 2.0** vs. digital coupon only) have >90% and >99% power, respectively (Table 4). We also provide power estimates for smaller effect sizes. The power was calculated using PASS software V15.0., with a two-tailed alpha of .025, resulting in a family-wise error rate of at most 0.05 for the primary outcome in the Aim 2. Due to an expected overall small number of individuals testing HIV- positive, we will not have power to detect potential differences between arms.

PROTECTION OF HUMAN SUBJECTS

A. RISKS TO HUMAN SUBJECTS

A1. HUMAN SUBJECTS INVOLVEMENT, CHARACTERISTICS, AND DESIGN.

A1a. Proposed human subject involvement. The protocol will include a 3-arm parallel, single blind, pragmatic randomized control trial of an online HIV digital messaging intervention (CHALO! 2.0) compared to an Attention-Matched Control, or a Digital Coupon only. Through online surveys, HIV testing utilization and results, and clinic visit data tracked by HST healthcare workers during the 12-week intervention period, and during the 15 months of follow-up, we will evaluate the outcomes for CHALO! 2.0.

A1b. Subject population characteristics. The 1000 MSM in the proposed trial will be composed of a diverse sample of individuals unaware of their current HIV status (e.g. never tested or tested >6 months ago and have been sexually active with men) recruited via MSM specific dating apps (Blued, Grindr), and via the most used general social media sites (Instagram) in an urban area with high rates of HIV (Mumbai, India). Currently, HIV rates for online-person recruited MSM in Mumbai are estimated at 5-7%, based on our recent studies (the only

such data available). All participants are expected to identify as Asian Indian and male.

A1c. Description and justification of sampling plan, recruitment and retention strategies and eligibility criteria.
Recruitment will be passive via online advertisement displayed to individuals on MSM dating apps (Grindr and Blued, and will include others if we find a new app emerging in popularity) or by targeted advertisements on Instagram to men who have LGBTQ/gay interests or keywords associated with their profiles. Due to technological advancements, the ads will be geographically limited to those potential participants accessing these sites from Mumbai or those who have indicated a Mumbai address on their social media profile. All advertisements will contain links directing potential participants contain links directing potential participants to a webpage with further information about the study and an eligibility screener. Eligible participants will be directly linked to an informed consent page (including an audio-video version of the informed consent),⁶³ and non-eligible participants will be directed to an exit page thanking them for their interest. Eligible participants who agree to participate after reading the informed consent will be directed to a baseline survey. All potential participants will provide a phone number associated with their WhatsApp account and an email address, and reply to a confirmation code (sent immediately to confirm the individual is real and not a bot or a computer program). Phone numbers will be checked against HST's registry by research staff to ensure participants aren't already receiving services through HST. Eligible participants will receive their incentive and be considered fully enrolled within 48 business hours.

Retention will be enhanced by (1)utilizing Whatsapp for intervention and online survey delivery since all incoming mobile phone calls text messages are free in India, which will allow participants to receive all study communications and will remove the burden for participants to appear go to a study site to complete the surveys (2) collecting information in the baseline assessment about whether and how peer-counselors should identify themselves when calling or texting (e.g., by name, "the research study," or the "CHALO! project"), particularly for participants who test HIV-positive, (3) providing incentives completing online surveys (at 0,3,6,12, 18 months) in increasing amounts (\$6.20, \$7.75, \$8.52, \$8.52, and \$9.30 respectively), (4) providing participants choices of incentives to broaden acceptability of incentives (PayTM – e-cash widely used in India, and connected to mobile number, or Amazon.co.in gift-code) (5) utilizing a drawing prize system of one in twenty \$15.50 incentives to reinforce online study assessment completion and minimize attrition (at 3,6,12,18 months) and being entered into a drawing at months 9 and 15 (for one of twenty \$15.50 incentives) for verifying or updating contact information.

This protocol aims to recruit a diverse sample of men who do not know their current HIV status (i.e., report that they have either never been tested for HIV, are unaware of HIV test results, or are HIV-negative with last HIV test greater than or equal to six months ago, and have engaged in anal sex since last HIV test). Therefore, inclusion criteria will be

(1) ≥18 years old; (2) live or work in the Mumbai metropolitan area, including Thane; (3) fluent in Hindi or English, (4) identify as cis male, (5) anal sex with men in past 1 year; (6) (a) report that they have either never tested for HIV, (b) are unaware of HIV test results, or (c) are HIV-negative with last HIV test >6 months ago and anal sex since last test; (7) able to provide and verify a WhatsApp mobile number and email address; (8) willing to answer online surveys for 18 months; and (9) have not participated in a prior HIV research study (by self-report).

We will exclude individuals who (1) are unwilling to consent/ assent to the study, (2) do not verify their WhatsApp account, and (3) have used services at HST within the past year.

A1d. Special vulnerable populations. We will not include fetuses, neonates, children, pregnant women, prisoners, or institutionalized individuals in the proposed research. Men who have sex with men are vulnerable due to their status as a stigmatized population in society and further stigmatization could be possible if their status as a participant in an HIV prevention intervention is revealed. In the following sections, we discuss these risks and procedures to minimize them and believe that the risks to participation in the proposed study are minimal.

A1e. Study group assignment procedures, and rationale for intervention's dose, frequency and administration. Subjects meeting all eligibility criteria will be randomized to one of three study arms. Participants will be assigned either to CHALO! 2.0 (intervention), to an Attention-Matched Control, or to a Digital Coupon for free HIV testing only arm. Randomization will occur in a random blocked design, stratified by HIV testing history (never tested/unaware of results vs. previously tested). To minimize bias in treatment group allocation, the data manager will store the allocation sequence using a password-protected file, and has no contact with study participants. Participants will receive automated messages with online

survey links to complete study assessments, and study staff extracting medical record/log data to ascertain linkage-to-care outcomes, will be blinded to treatment group allocation and will have no contact with study participants.

During the 12-weeks intervention period, participants assigned to either CHALO! 2.0 (intervention) or the Attention-Matched Control (AM) arm will be exposed to twice-weekly digital messaging, including text, brief videos, inform graphics, etc. via an online messaging site. However, the digital message for participants in the CHALO! 2.0 arm will include information regarding HIV testing, accessing treatment and prevention care with a focus on targeting information, motivation, and behavioral skills, while the information in the AM arm will focus on general health topics (e.g., diabetes, obesity, nutrition, exercise). Participants in the digital coupon only arm will not receive any messages aside from the reminders to complete study assessments. We are providing twice weekly contents as this was determined in the past to be acceptable, not intrusive and higher frequency may actually be detrimental.

Participants in all three arms will receive a digital coupon for free rapid HIV testing or 4th generation serum testing (per participant choice), have access to a website listing the testing sites where the coupon is redeemable across Mumbai, care information for treatment and prevention, and have contact information to get in contact through SMT with HST's online peer counselors.

Through online surveys, HIV testing utilization and results, and clinic visit data tracked by HST navigators/health workers during the 12-week intervention period, and during the 15 months of follow-up, we will evaluate the CHALO! 2.0 exposure outcomes.

A2. SOURCES OF MATERIALS.

The HST team will collect online survey data (at baseline, 3, 6, 12, and 18 months), HIV testing utilization and results (throughout the 18 months), and clinic visit data tracked by HST navigators/health workers through existing linkage to care and tracking protocols at HST (over the 18-month tracking period).

Online Surveys. Avegen Health Machine (HM), an online web surveys software, will be used to collect self-reported data from participants on their sexual behaviors, sociodemographics, HIV testing history, how they self-identify with regards to sexuality, HIV knowledge, motivation for testing, intention to obtain HIV test, self-efficacy for testing and care, HIV and internalized sexual minority stigmas, and HIV prevention knowledge.

Personalized Digital Coupon use data (HIV testing data): All participants, after verifying their contact information will receive a personalized digital coupon consisting of a QR barcode and number through a Whatsapp message and email. The coupon will be linked to their study-id and mobile number, preassigned by the data manager. Once a client presents the coupon at any testing site, the tester-counselor (at HST sites) or lab technician (at the private lab sites) will scan the coupon or enter the coupon code using an online coupon management system, which will register the coupon as being used with time, date, and location of the scan saved by the coupon software in their online system. On a twice weekly basis, the data manager will download the coupon use data and merge it into the Avegen HM database.

This system will also alert study staff that a coupon was used with information about which coupon, so that study staff can follow-up with clients if needed about their results. If the coupon is used at HST, the tester/counselor will enter test results directly into a front-end HIV testing result form on Avegen HM (coupon-code and associated test result); if the coupon is used at a private lab, study staff will retrieve results from the lab's online portal, and then enter the test results into a front-end HIV testing result form on Avegen HM.

This approach has been generally used previously, including in a recent feasibility pilot by our private laboratory partner, and will enable real-time monitoring of test results, and accurate follow-up for clients.

Lab HIV testing data: Additionally, HST currently collects and verifies mobile phone numbers for clients coming in for testing to enable follow-up and linkage-to-care and as a requirement per Indian guidelines and requirements for testing. Subjects will only be able to receive the free test at the private lab or HIV self-test if they show the coupon. These steps will help ensure thorough assessment of our primary outcome and facilitate appropriate follow-up.

Linkage-to-care outcomes for HIV negative and positive individuals will be abstracted from HST's healthcare worker log, which contains information about linkage status and outcomes (HIV treatment registration, ART initiation, follow-up) or from HST's counseling and clinic utilization records which are housed on a computerized information system (CIS) at HST. Data from the HST healthcare worker log and the CIS can be linked to an individual's mobile phone number which will be how we match a participant's use of HST services. The data manager at HST on a monthly basis, will scan and match participant phone numbers to those in CIS; for any matches, that data will be extracted and merged into the Avegen HM database. The healthcare worker log also contains information about linkage/referrals to private HIV treatment clinics and for primary care/PrEP. Currently, HST refers clients interested in PrEP to two providers in Mumbai (vetted by HST to

provide MSM competent services). HST will also begin offering PrEP this summer to its patients, and will thus be available moving forward for all HST clients, including study participants.

Whatsapp Business Analytics Data. This platform will be used to preschedule the automated messages participants will receive in the CHALO! and attentional control arms and it enables us to download data from the Whatsapp business analytics platform to merge into the study database on Avegen HM. This data will contain information for CHALO! and attention matched control arms about if each message/content was received and if the message/contents was viewed. This will give us a crude measure of exposure (or engagement with intervention contents) to enable calculation of “dose received” and associate this data with outcomes. The data manager will download this data and merge it into the Avegen HM database.

Online Peer-Counselors Interaction data. Participants will be able to connect via Whatsapp to online peer-counselors at HST to receive support, answers questions, or referrals for linkage services. For each of the online-peer counselors, communication related process measures will be collected by downloading their message- and voice-call history and merge this data into the final study database in Avegen HM to examine potential associations with study outcomes as mobile phone numbers can be linked to individual participant data.

Study Webpage visit data (process data). All participants will be given a personalized link (e.g., using Bit.ly link shortener) to identical informational webpages (one webpage per arm) listing testing sites where the digital coupon can be used, contact information for the online Peer-Counselor, and other MSM specific health and wellness services offered by HST (e.g., mental health counseling, crisis support, hotline). The webpages will also have google analytics attached to the website to monitor traffic and visits. The use of personalized links and study- and arm-specific webpages will enable us to collect process data on website visits and assess overall web visit traffic by study arm as well as determine frequency of clicks on the individual links. While this individual link data cannot be attributed to one individual due to current limitations and privacy protections of tracking ability by Google Analytics and Bitly, allows for exploration of whether certain individual's links were clicked through more often than others and in exploratory analysis, compare this by study arm.

